9.3. Prohibited Medications

Other anticancer treatments are not allowed in this study. The medications listed in [Table 19](#) are known or suspected to impact the bioavailability, pharmacokinetic and potentially safety as well as efficacy profile of the study medications. The concomitant use of these medications with study therapy is therefore prohibited.

Table 19: Prohibited Concomitant Medications

| |
|--|
| Antineoplastic Therapy |
| 
 • Cytotoxic chemotherapy • Biological therapy (including but not limited to: therapeutic antibodies and cytokines) • Radiation therapy¹ • Investigational agents |
| Immunotherapy |
| 
 • Immunotherapy for any indication • Live, attenuated vaccines (including but not limited to the following: measles, mumps, rubella, chicken pox, yellow fever, seasonal flu, H1N1 flu, rabies, BCG, and typhoid)² |
| Immunosuppressive agents |
| 
 • Immunosuppressive agents (except to treat a drug-related adverse event) |
| Anticoagulants |
| 
 • Warfarin or other Vitamin K antagonists |
| Glucocorticoids |
| 
 • Glucocorticoids used chronically (≥ 14 days)^{3,4} • Systemic corticosteroids > 10 mg daily prednisone equivalent (except as stated in Nivolumab IB or to treat a drug-related adverse event). |

¹ Palliative radiation therapy may be allowed after consultation and in agreement with the study sponsor.

² Live, attenuated vaccines are prohibited 30 days prior to the first dose of study therapy and throughout study participation.

³ Chronic (≥ 14 days) use of glucocorticoid for adrenal replacement is allowed.

⁴ The use of physiologic doses of corticosteroids may be approved after consultation and in agreement with the study sponsor.

9.4. Concomitant Medications to be Avoided, or to be Used with Caution

The bioavailability and in consequence the safety as well as efficacy profile of the medications listed in [Table 20](#) may be altered when co-administrated with study therapy. Therefore, these medications should be avoided, or should be administered with caution concomitantly with study therapy. Instructions for medications to be used with precaution are also provided in [Attachment 7](#).

Table 20: Concomitant Medications to be Avoided or to be Used with Caution

| |
|---|
| CYP3A4 /5 Inducers and Inhibitors |
| 
 • Strong and moderate CYP3A4/5 inducers¹ • Strong and moderate CYP3A4/5 inhibitors¹ • Grapefruit and Seville oranges |
| QT-Prolonging Agents |
| 
 • Medications known to cause Torsade's des Pointes² |
| Supplements |
| 
 • Fish oil • Vitamin E preparations |
| P-gp Substrates |
| 
 • P-gp substrates with narrow therapeutic index (eg, Digoxin) |
| Anticoagulants and Antiplatelet Agents³ |
| 
 • Other anticoagulants then listed in Table 19 • Other medication that inhibit platelet function then listed in Table 19 |
| Surgical intervention |
| 
 • held at least 3 to 7 days pre- and post-surgery depending upon the type of surgery and the risk of bleeding |

¹ For a listing of CYP3A4/5 inhibitors and inducers see [Attachment 8](#) and <http://medicine.iupui.edu/clinpharm/ddis/main-table>.

² For a listing of medications that cause QT prolongation see http://www.azcert.org/medical-pros/drug-lists/list-01.cfm?sort=Generic_name.

³ Subjects requiring the initiation of therapeutic anticoagulation therapy (other than warfarin or a vitamin K antagonist) during the course of the study should have treatment with ibrutinib held, the sponsor's medical monitor should be contacted, and ibrutinib should not be restarted until the subject is clinically stable and the re-initiation of ibrutinib is approved by the sponsor's medical monitor. Subjects should be observed closely for signs and symptoms of bleeding. No dose reduction is required when study drug is restarted.

9.5. Subsequent Therapies

Administration of any other antineoplastic therapy, for reasons other than progressive disease is strongly discouraged until progressive disease is established according to the criteria described in [Attachment 6](#). After progressive disease is established, subsequent therapy is permitted at the investigator's discretion. Subsequent therapy (including start date, end date, and best response) should be documented in the appropriate section of the eCRF.

10. STUDY EVALUATIONS

10.1. Efficacy (Assessment of Disease Response and Progressive Disease)

Efficacy assessments will be performed as outlined in Time and Events Schedule ([Table 1](#)). These assessments are to be conducted until disease progression (even if subsequent therapy is started prior to objective disease progression), withdrawal of consent from study participation, or the end of study. For subjects who discontinue study drug before disease progression is documented, disease assessments will continue in the Follow-up Period at least every 6 months until disease progression is documented or the start of subsequent therapy. The determination of disease status for continuation of treatment will be assessed by the investigator at the site based on the results of the efficacy assessments; the results will be recorded in the eCRF. Radiological and PET scans performed prior to the database lock for the final analysis may be transferred to the independent imaging laboratory for storage; the scans may be reviewed, if deemed necessary.

For all subjects, as soon as disease progression is confirmed the sponsor's study lead should be informed immediately. A tumor biopsy should be collected for biomarker evaluations at progression, depending on the indication and if clinically feasible.

The detailed description of efficacy measurements that will be obtained during the study are provided in [Attachment 5](#). At all times, identical methodology should be used for disease assessment at baseline and throughout the course of the study.

The investigator will perform tests that will allow evaluation of response to therapy according to corresponding disease criteria in [Table 21](#).

Table 21: Response Criteria

| Criteria | PART A | PART B | Attachment |
|--|---|----------------------------------|------------|
| IWCLL ¹ | Subjects with CLL | Cohort B1 (CLL) | 6.1 |
| Response Assessment of Non-Hodgkin Lymphoma² | Subjects with B-cell NHL, including SLL | Cohorts B1 (SLL), B2, B3, and B4 | 6.2 |

¹ International Workshop on Chronic Lymphocytic Leukemia (Hallek 2008)²³

² Recommendations for Initial Evaluation, staging and Response Assessment of Hodgkin and Non-Hodgkin Lymphoma: The Lugano Classification (Cheson 2014)¹²

The efficacy endpoints are defined as follows, based on the IWCLL or the Lugano Classification by Cheson (2014),¹² as appropriate for the disease:

- Overall response rate, which is defined as the proportion of evaluable subjects who achieve CR or PR, as assessed by the investigators,
- Duration of response will be calculated from the date of initial documentation of a response (CR, or PR) to the date of first documented evidence of progressive disease (or relapse for subjects who experience CR during the study) or death. Subjects who are progression-free and alive or have unknown status will be censored at the last tumor assessment.
- Progression-free survival is defined as the duration from the date of first dose of study drug until the date of first documented evidence of progressive disease (or relapse for subjects who experience CR during the study) or death, whichever comes first. Subjects who are progression-free and alive or have unknown status will be censored at the last tumor assessment.
- Overall survival is measured from the date of first dose of study drug to the date of the subject's death. If the subject is alive or the vital status is unknown, the subject will be censored at the date the subject was last known to be alive.

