| CT imaging (neck, chest, abdomen, and pelvis) with oral and IV contrast | CT scan with IV contrast (oral if IV is contraindicated) of the neck, chest, abdomen, and pelvis and any other disease sites present at Screening. MRI only for disease sites that cannot be adequately imaged using CT. Brain MRI required only if clinically indicated. | X (imaging part of standard assessments; within 6 weeks prior to dosing is acceptable) | | Q5cycles (starting cycle 5) for first 15 months, thereafter Q12 cycles until PD. After clinical cutoff, disease assessments to be performed Q12 cycles or per local standards (but at a minimum of Q26 weeks). To be performed at the time of atypical responses 'tumor flare'. The same imaging technique used at Screening should be used throughout the study. Results are preferably available before start of treatment in the following cycle. During Follow-up, to be performed at PD and at least Q6 months up to PD or start of subsequent therapy | |
| Whole body FDG-PET scan | For NHL assessments, PET scan at baseline is recommended but not mandatory. Maximal tumor reduction: eg CR or 2 consecutive CT scans showing no further tumor reduction. | X | | at the time of maximal tumor reduction, relapse from CR | |
| Evaluation of other sites of disease | May be performed by radiological imaging, physical examination, or other procedures as necessary | as clinically indicated | | as clinically indicated, using the same method of assessment as used at Screening | |

| | Notes | Screening Period | Treatment Period (14 day cycles) | | | Follow-up Period ^a |
|---|---|---|---|--------------------------|-----|-------------------------------|
| | | up to 28 days before start of any study treatment | BASELINE ASSESSMENT CID1 (without run-in phase) CID-7 (with run-in phase) | Day 1, subsequent cycles | EOT | Q3m |

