Preliminary activity and clinical response will be evaluated every 5 cycles for the first 15 months, thereafter every 12 cycles until progression, at the end of treatment, and every 6 months in follow-up, in the event the subject has not progressed while on therapy and did not start subsequent therapy. Lymphoma including Richter syndrome will be evaluated for response according to the Lugano Classification (Cheson 2014);¹² CLL will be evaluated according to International Workshop on Chronic Lymphocytic Leukemia (IWCLL) (Hallek 2008), see Section 10.1.²³ Identical methodology should be used for disease assessment at baseline and throughout the course of the study.

Subjects will be assigned to receive oral daily doses of ibrutinib (self-administered) in combination with intravenous nivolumab on Day 1 of each cycle starting from Dose Level 1 ([Table 4](#)). In Cohort B1 and B2, to assess pharmacokinetic and pharmacodynamic characteristics of ibrutinib monotherapy, ibrutinib will be given at the recommended Phase 2 dose over an initial period of seven days prior to the first dose of nivolumab (Day -7 to -1). Refer to the Dosage and Administration schedule (Section 6) for further detail. Protocol specified treatment modifications for ibrutinib and nivolumab will be implemented as necessary (Section 6.4). Additional dosing or schedule changes for ibrutinib or nivolumab can be requested by the Study Evaluation Team (SET) based on preliminary clinical data during dose optimization. Doses may be held or reduced based on the severity of and the recovery from previous toxicity. Dose re-escalation may be allowed after

recovery from toxicity following consultation with the Sponsor. In Part A intra-patient dose escalation may be requested by the investigator and discussed with the medical monitor once a subsequent higher combination dose has been declared acceptable by the SET for subjects who (1) have received at least 4 cycles of combination treatment at the assigned dose level, and (2) have not experienced a DLT or therapy-related SAE. Subjects whose dose has been escalated will not be considered for the safety evaluation in the subsequent dose level and the determination of the RP2D.

The study treatment will be continued until:

- documented confirmed disease progression (except in cases of clinical improvement/stability; see Section 11.2)
- unacceptable toxicity
- intercurrent illness that prevents further administration of treatment

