Subjects who discontinue treatment prior to disease progression (for other reasons such as an adverse event) must continue to have regularly scheduled CT scans/efficacy assessments every 10 weeks up to 15 months after the start of study drug. Thereafter, scan will be performed every 24 weeks until disease progression, or death, or the end of the study, whichever occurs first. It is important that instances of progressive disease be reported to the sponsor's medical monitor within 24 hours by means of a form provided by the sponsor (see Contact Information pages provided separately).

Definition of Measurable and Assessable Disease

Eligible subjects must have at least 1 measurable site of disease. Measurable sites of disease are defined as lymph nodes, lymph node masses, or extranodal sites of lymphoma. Each measurable site of disease must be greater than 1.5 cm in the long axis regardless of short axis measurement or greater than 1.0 cm in the short axis regardless of long axis measurement, and clearly measurable in 2 perpendicular dimensions. Measurement must be determined by imaging evaluation. All other sites of disease are considered assessable, but not measurable.

Up to 6 measurable sites of disease, clearly measurable in 2 perpendicular dimensions, will be followed for each subject. Measurable sites of disease should be chosen such that they are representative of the subject's disease (this includes splenic and extranodal disease). If there are lymph nodes or lymph node masses in the mediastinum or retroperitoneum larger than 1.5 cm in 2 perpendicular dimensions, at least 1 lymph node mass from each region should always be included. In addition, selection of measurable lesions should be from as disparate regions of the body as possible.

All other sites of disease will be considered assessable. Assessable disease includes objective evidence of disease that is identified by radiological imaging, physical examination, or other procedures as necessary, but is not measurable as defined above. Examples of assessable disease include bone lesions; mucosal lesions in the GI tract; effusions; pleural, peritoneal, or bowel wall thickening; disease limited to bone marrow; and groups of lymph nodes that are not measurable but are thought to represent lymphoma. In addition, if more than 6 sites of disease are measurable, these other sites of measurable disease may be included as assessable disease.

Positron Emission Tomography (PET Scan)

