4.2. Primary Efficacy Endpoint(s)

4.2.1. Definition

The primary endpoint is ORR, defined as the proportion of subjects who achieve partial response or better [PR(+L) or better], as assessed by the investigators at or prior to initiation of subsequent anti-cancer therapy. The primary efficacy analysis of ORR will be conducted at performed 6 months after the last subject has received the first dose of study medication, or earlier if that subject discontinues study therapy. The analysis will be based on the all-treated population.

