4.3.3. Progression-free Survival and Overall Survival

Definition

PFS is defined as the interval between the date of first dose of study drug and the date of first documented evidence of PD (or relapse for subjects who experience CR during the study) or

death, whichever comes first. Subjects who are progression-free and alive, or have unknown status will be censored at the last adequate disease assessment.

OS is defined as the interval between the date of the first dose of study drug and the date of the subject's death from any cause. If the subject is alive at the time of the cut-off, it will be censored at the last known alive date (the last date among visit date, AE start and end dates, treatment date, disease assessment date, and survival follow up date, and if available, survival sweep date, etc.).

Analysis method

Similar analyses will be applied to OS and PFS as those used for duration of response. The distribution of PFS and OS will be estimated using the Kaplan-Meier method.

The primary analysis of PFS will be based on assessments by investigator. The reason of censoring will be summarized for OS and PFS. The median follow-up duration will be provided. Follow-up duration is defined as OS with reversed censoring, i.e., subject who died will be censored. The Kaplan-Meier method will be used to estimate the median follow-up.

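### Section 10.1 both continues and stops disease assessment at subsequent therapy, and PFS and DOR have no matching rule, so their censoring can depend on later outcome, with bias in either direction

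*Protocol*

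**What the plan says.** **Assessment after study drug stops.** The protocol gives two answers.

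- *Continue past subsequent therapy.* The opening of Section 10.1 runs assessments to progression, consent withdrawal or end of study, "even if subsequent therapy is started prior to objective disease progression". Attachment 5 says that subjects who stop treatment before progression "must continue to have regularly scheduled CT scans/efficacy assessments every 10 weeks up to 15 months after the start of study drug", then every 24 weeks until progression, death or end of study. It does not mention subsequent therapy.
- *Stop at subsequent therapy.* The next sentence on follow-up in Section 10.1 has subjects off study drug assessed at least every 6 months "until disease progression is documented or the start of subsequent therapy". The CT row of Table 1 agrees: "During Follow-up, to be performed at PD and at least Q6 months up to PD or start of subsequent therapy". Section 3.1 schedules 6-monthly follow-up assessment "in the event the subject has not progressed while on therapy and did not start subsequent therapy".

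**Endpoints.** Protocol Section 10.1 and SAP 4.3.1 and 4.3.3 define DOR and PFS by progression (or relapse after CR) or death. In the SAP, subjects alive and progression-free, or of unknown status, "will be censored at the last adequate disease assessment". None of these sections says what to do when subsequent therapy starts before progression. SAP 4.2.1 does set that boundary for ORR, which counts response "as assessed by the investigators at or prior to initiation of subsequent anti-cancer therapy".

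**Related text.** Protocol Section 9.5 strongly discourages other antineoplastic therapy before progression and requires its start date in the eCRF. No expected frequency is given.

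**The concern.** The two sentences of Section 10.1 cannot be separated by population. Section 9.3 bars other anticancer treatment during study therapy, so a subject who has started subsequent therapy is almost always off study drug. The second sentence therefore covers nearly everyone that the parenthesis in the first is about. Sites can follow different rules and each be compliant with part of the protocol.

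The interval matters too. Scanning every 10 weeks satisfies a minimum of every 6 months, but a site that scans 6-monthly complies with Section 10.1 and breaches Attachment 5. Wider gaps also document progression later.

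At stake are 1-year PFS and DOR, both secondary objectives (Section 2.1). The primary Part B objective is framed against historical results, and PFS or DOR with an undefined switching rule is hard to set beside any external figure.

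**Working it through.** **1. The plan's own figure.** The only sample-size figure is 32 evaluable subjects per Part B cohort (ORR 20% v 38%, one-sided 0.1, power at least 0.8). Exact binomial: with n = 32 and at least 10 responses, alpha is 0.0898 and power 0.833; n = 31 gives power 0.799. The figure reproduces and does not involve PFS or DOR.

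**2. The mechanism under the stop rule.** Let a subject's last scan be at time s, the switch at w > s, and scans then stop.

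- Progression after w: not observed.
- Death at d > w: a PFS event at d. The subject counts as progression-free from s to d, including time on the next therapy.
- Alive at cutoff: censored at s.

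Whether a switcher is censored at s or kept to d therefore depends on what happens after s. Two forces oppose each other. Unseen progressions push the estimate up. Keeping switchers who die while removing those who live pulls it down. DOR has the same events and censoring, counted from first response. Under the continue rule this censoring does not arise.

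**3. Size for 1-year PFS.** Kaplan-Meier simulation, 200,000 subjects per scenario, scans at week 8, then every 10 weeks to about 15 months, then every 24 weeks. The following are assumptions, not document figures: exponential times, 18 months of accrual, median progression/death of 4/12, 12/36 or 30/60 months, nominal switching of 5%, 15% or 30%, and post-switch hazard ratios (HR) of 0.5 to 4. At nominal 30% the simulated share that switched was 35%, 25% and 16% for the three pairs of medians.

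A = scans continue to progression. B = scans stop at the switch, later deaths count. C = progression and death both censored at the switch.

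| Switching | Medians (mo) | HR progression / death | A | B | B - A (points) | C |
|---|---|---|---|---|---|---|
| 30% | 4/12 | 4 / 1 | 2.9% | 9.1% | +6.2 | 6.5% |
| 30% | 12/36 | 4 / 1 | 34.2% | 39.9% | +5.7 | 41.2% |
| 30% | 4/12 | 1 / 1 | 7.2% | 9.4% | +2.2 | 6.7% |
| 30% | 12/36 | 1 / 1 | 41.4% | 39.7% | -1.7 | 41.0% |
| 30% | 30/60 | 1 / 1 | 67.0% | 66.1% | -0.9 | 66.9% |
| 30% | 12/36 | 0.5 / 0.5 | 44.9% | 40.3% | -4.6 | 41.0% |
| 5% | 4/12 | 4 / 1 | 6.3% | 7.3% | +1.0 | 7.0% |
| 5% | 4/12 | 0.5 / 0.5 | 8.2% | 7.4% | -0.8 | 7.1% |

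Over all scenarios B - A runs from about -4.6 to +6.2 points. At 5% switching it stays within about 1 point.

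**4. Scale.** The binomial standard error with 35 subjects is sqrt(p(1-p)/35): 8.3 points at p = 0.41, 7.9 at 0.67, 4.3 at 0.07 and 2.8 at 0.029. The shift is smaller than one standard error at moderate PFS, but can exceed it when 1-year PFS is very low.

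**5. Why sensitivity analyses are needed.** A second simulation (medians 8/14 months, 22% switching, hazards doubled after the switch, all assumed) gave 1-year PFS of 15.7% followed to progression, 17.5% with scans stopped and deaths counted, 18.3% censored at the switch, and 11.9% with the switch as an event. In that case the last two bracket the followed value.

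**The case against.** A reader might infer that PFS and DOR are overstated, because early switching usually signals poor prognosis. The documents do not support that. They give no switching rate and no post-switch hazards, and the sign reverses when the next therapy works, or at the longer medians with unchanged hazards.

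A reader might also infer that PFS and DOR must adopt the ORR boundary. That does not follow. ORR asks whether a response is attributable to study drug, whereas counting progression or death regardless of new therapy is a coherent definition that matches the first sentence of Section 10.1 and Attachment 5. Nor does censoring at the switch remove informative censoring: in the 12/36-month, HR 4 / 1 row, C (41.2%) is further from A (34.2%) than B (39.9%) is; in the first row it is closer.

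Three further arguments limit the consequence, and they stand. Switching before progression is discouraged and may be rare. PFS and DOR are single-arm, descriptive, and headed exploratory secondary in the SAP; no test or decision rule uses them. The stated reason for Amendment 7 is that primary and secondary objectives have already been analyzed and published, so a changed main rule would be post hoc.

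None of this removes the contradiction in current text, or the mismatch between the stop rule and an endpoint that needs scans to continue.

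**Conclusion.** The concern holds in limited form. The assessment rules conflict in the current protocol on both stopping point and interval, and neither document says how PFS and DOR handle subsequent therapy. Where the stop rule is followed, censoring depends on later outcome. The resulting error in 1-year PFS has no predictable sign: about -5 to +6 points with nominal switching of up to 30%, and about 1 point or less at 5%, all under assumed hazards, medians and accrual. For DOR the mechanism is the same but the size was not estimated. The primary ORR analysis and the sample size are untouched.

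**What to change.** 1. **Protocol.** Reconcile Section 10.1, Table 1, Section 3.1 and Attachment 5 to one statement of whether, and how often, disease is assessed after study drug stops and after subsequent therapy starts.

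2. **SAP 4.3.1 and 4.3.3.** State one PFS/DOR rule that matches that schedule and treats later progression and later death alike. Either follow both to event, with scans continued, or censor both at the last adequate assessment on or before subsequent therapy.

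3. **Sensitivity analyses.** Report the rule not chosen, and a version with start of subsequent therapy as an event. Give the number of switchers before progression in each cohort and how many were scanned afterwards.

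The start dates are already collected under Section 9.5, so the SAP change needs no new data. Scans not done after a switch cannot be recovered, so for those subjects the follow-to-event version stays incomplete and should be labeled so. If the main PFS and DOR results have already been reported, present the added analyses as post hoc. The cost is wording and a little more analysis work.
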